## 9.2.3.3 Vital signs and body weight

Summary statistics of vital signs (diastolic blood pressure, systolic blood pressure, pulse rate, body temperature) and body weight at each assessment timepoint and their changes from baseline will be computed for each ARM.

#### 9.3 Significance level

The analysis on non-inferiority will be performed with a two-tailed confidence interval of 90%. A two-tailed significance level of 5% will be used for all other analyses unless specified otherwise.

#### 9.4 Number of subjects

• Target number of subjects to be enrolled

300 subjects (target number of subjects to be enrolled in each study site is shown in the list of study sites.)

• Randomization ratio

Subjects will be stratified by countries (Japan, South Korea, and Taiwan) as a stratification factor, and for each stratum, randomized to ARM-2 and ARM-3 at the ratio of 1:1.

## 9.4.1 Sample size selection

Assuming that the SDAI remission rate is 30% for both ARM-2 and ARM-3, and the noninferiority margin is -15%, the number of subjects required for the lower bound of a twotailed 90% confidence interval for the intergroup difference in SDAI remission rate to exceed the non-inferiority margin at 80% power of detection would be 220 subjects in total (110 in each group).

Past reports suggest that the remission rate of MTX monotherapy is about 15%. Also, it has been reported that about 10% of patients cannot continuously receive MTX  $\geq$ 10 mg/week (Atsumi T, et al. 2016: 75-83). Thus, in order to randomize 220 subjects between ARM-2 and ARM-3, 288 subjects need to be enrolled, and considering some dropouts, a sample size of 300 subjects was selected as the target number of subjects to be enrolled.

<Justification for the estimated SDAI remission rate in ADA/MTX-Reduced Dose Group (ARM-3)>

The estimated SDAI remission rate in ARM-3 was calculated in reference to the results of the MTX Monotherapy  $\rightarrow$  ADA+MTX Group in HOPEFUL 1 Study in which Japanese MTX naïve patients receiving ADA+MTX or MTX alone for 26 weeks, and then, all subjects receiving ADA+MTX for another 26 weeks (Takeuchi T, et al. 2014: 536-43). Since the maximum dosage of MTX in HOPEFUL 1 Study was 8 mg/week (6.6±0.8 mg/week: Mean±SD), the results cannot be directly extrapolated to this study in which the maximum dosage of MTX up to Week 24 will be 16 mg/week; yet, the results would be appropriate to use as a reference for the SDAI remission rate in ARM-3 in which the dosage of MTX will be reduced to 6 to 8 mg/week from Week 24 onward. ARM-3 is designed for patients who have not achieved to SDAI remission at Week 24; thus, assuming that the subjects with SDAI remission at Week 26 in HOPEFUL 1 Study (20 subjects = 163 subjects × 12%) remain to be remission at Week 52, the Week-52 SDAI remission rate among the subjects with SDAI non-remission at Week 26 was calculated to be 31.5% [45/143 subjects, that is (65 subjects - 20 subjects)/(163 subjects -20 subjects)]. Therefore, the SDAI remission rate in ARM-3 was assumed to be 30%.

<Justification for the estimated SDAI remission rate of  $\leq$ 3.3 in ARM-2 (ADA/MTX-MTD Group)>

There is no data on SDAI remission rate on ADA as add-on therapy given in Japanese patients previously receiving adequate amount of MTX for  $\geq 6$  months. However, it has been reported that there was no difference in efficacy of MTX at dosage  $\geq 10$  mg/week in a clinical study in which Western MTX naïve patients started concomitantly receiving ADA

and MTX at the same time (Burmester GR, et al. 2015:1037-44), and that there was no difference in DAS28-ESR remission rate between a low-dose concomitant MTX group (8 to  $\leq$ 12 mg/week) and high-dose concomitant MTX group (>12 to 16 mg/week) according to a stratified analysis on a study in which Japanese MTX naïve patients started concomitantly receiving certolizumab pegol (CZP) and MTX at the same time (Atsumi T, et al. 2016: 75-83). Thus, the SDAI remission rate in ARM-2 was assumed to be 30% just like in ARM-3.

<Justification for the non-inferiority margin>

Both ARM-2 and ARM-3 are designed for patients who have not achieved to SDAI remission at Week 24; thus, assuming the SDAI remission rate is 0% in patients continuously receiving MTX alone without adding bDMARDs, a half of the SDAI remission rate of 30% in ARM-2, which is 15%, was selected as a non-inferiority margin.

<Justification for the estimated SDAI remission rate in MTX Monotherapy Group> In studies conducted in Japanese MTX naïve patients, the SDAI remission rate in 6 months of treatment with MTX alone was 12.3% (21/171 subjects) and 29.3% (46/157 subjects) (Atsumi T, et al. 2016: 75-83, Takeuchi T, et al. 2014: 536-43). Also, in studies conducted in Western MTX naïve patients, the SDAI remission rate in 6 months of treatment with MTX alone was 11.2% (13/116 subjects) and 16.4% (47/287 subjects) (Emery P, et al. 2015: 19-26, Smolen JS, et al. 2016: 1081-91.). Accordingly, the remission rate of MTX monotherapy was estimated to be 15%.

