## 9 Statistical analysis

## 9.1 Statistical analysis set

## (1) Full analysis set (FAS)

FAS is defined as a group of subjects who receive study drug (MTX) and have evaluable efficacy data at 1 or more time points following the administration of study drug. Modified FAS (mFAS) is defined as a group of subjects who are randomized after Week 24, receive study drug (ADA), and have evaluable efficacy endpoint at 1 or more time points following the administration of study drug.

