#### 9.6 Handling of study data

Subjects with missing data at an assessment timepoint of SDAI remission, ACR20, ACR50, and ACR70 response, HAQ remission, and structural remission due to study discontinuation or other relevant reasons will be considered as a "non-responder" at the specific timepoint. Any missing data on SDAI, CDAI, DAS28-ESR, and DAS28-CRP will be considered as missing at the specific timepoint. A missing data on the assessment of SDAI, CDAI, DAS28-

ESR, DAS28-CRP, and mTSS will be complemented with the last observation carried forward (LOCF).

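### The inputs in Protocol 9.4.1 need about 114 to 117 subjects per arm for 80% power, not 110; 220 gives about 78 to 79%, and 300 enrolled leaves almost no room for dropout

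*Protocol*

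**What the plan says.** Protocol 9.4.1 sizes the trial on "the lower bound of a twotailed 90% confidence interval for the intergroup difference in SDAI remission rate" exceeding -15%, with 30% remission assumed in both arms. It states that the number required "at 80% power of detection would be 220 subjects in total (110 in each group"). Protocol 9.3 gives the same confidence level: "The analysis on non-inferiority will be performed with a two-tailed confidence interval of 90"%. Protocol 9.4 sets 1:1 allocation. No formula, software or interval method is named for the calculation.

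The section then takes 15% as the share in remission on MTX alone at Week 24 and 10% as the share who cannot stay on at least 10 mg/week; neither group is randomized. It concludes that "in order to randomize 220 subjects between ARM-2 and ARM-3, 288 subjects need to be enrolled, and considering some dropouts", the target becomes 300. No dropout rate is given.

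Two other rules bear on what dropout means here. Under Protocol 9.1, a randomized subject enters mFAS only after receiving ADA, and must "have evaluable efficacy endpoint at 1 or more time points following the administration of study drug". Under Protocol 9.6, a subject whose remission status is missing "due to study discontinuation or other relevant reasons will be considered as a" non-responder.

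**The concern.** The stated number is smaller than the stated inputs produce, so the claimed 80% power is slightly too high for 220 subjects. The same 220 is carried into the enrolment calculation. If the number to randomize is too low, so is the 288 derived from it, and part or all of the step from 288 to 300 is needed to reach 80% power, not to absorb losses. A reader of 9.4.1 would believe the trial has 80% power plus a dropout allowance, when on the protocol's own inputs it has about 80% and almost no allowance. Protocol 9.5 lists too few subjects assigned to ARM-2 or ARM-3 among the grounds for stopping the study, so the required number should be right.

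**Working it through.** **Inputs (Protocol 9.3, 9.4, 9.4.1).** Remission 0.30 in each arm, true difference 0, margin 0.15, lower limit of a two-sided 90% interval (z = 1.645), power 80% (z = 0.842), 1:1 allocation.

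**Required number, unpooled formula.** n per arm = (1.645 + 0.842)² × (0.3×0.7 + 0.3×0.7) / 0.15² = 115.4, so 116 per arm and 232 in total. The stated 110 is not reproduced.

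**Power at the stated number.** Power = Φ(0.15/√(0.42/n) − 1.645). At n = 110 this is 78.3%; at 115, 79.9%; at 116, 80.2%.

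**Does the choice of interval explain 110?** Power by full binomial enumeration with 30% in both arms, and enrolment as 2n/0.765 (derived below):

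| Interval | Power at 110 per arm | First n per arm with 80% | Enrolled |
|---|---|---|---|
| n−1 variance | 78.4% | 117 | 306 |
| Wald | 78.8% | 116 | 304 |
| Farrington-Manning score | 79.0% | 115 | 301 |
| Agresti-Caffo | 79.3% | 114 | 299 |
| Newcombe | 79.4% | 114 | 299 |

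None reaches 80% at 110. A continuity correction moves further away (about 74% at 110), and a one-sided 0.025 level needs 147 per arm. The nearest figure found was 108, from a continuity-corrected superiority formula for 30% versus 15%, which is not the stated design.

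**Enrolment, plan's figure first.** The share randomized is (1 − 0.15) × (1 − 0.10) = 0.765. 220/0.765 = 287.6, so the stated 288 is reproduced. The protocol then adds 12 to reach 300.

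**Same step with the corrected number.** 228/0.765 = 298.04, so 299. 232/0.765 = 303.3, so 304. That is 11 to 16 more than 288, against the 12 added.

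**What 300 delivers.** 300 × 0.765 = 229.5 randomized, about 114.75 per arm, and 79.8% power by the unpooled formula. This is 1.5 above 228 and 2.5 below 232.

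**Further losses.** The documents give no rate, so 5% is an assumption. If 5% more are lost before randomization or never enter mFAS, 229.5 × 0.95 = 218 remain and power is 78.0%.

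**Losses kept in mFAS as non-responders, equal in both arms.** The rate becomes 0.3 × (1 − d). At 110 per arm, power is 79.4% for d = 5% and 80.5% for d = 10%. Such dropouts do not lower nominal power.

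**Sensitivity to Week 24 remission.** In the studies 9.4.1 cites, six-month remission on MTX alone "was 12.3% (21/171 subjects) and 29.3% (46/157 subjects") in Japanese patients and "was 11.2% (13/116 subjects) and 16.4% (47/287 subjects") in Western patients. With 300 × (1 − r) × 0.90 randomized:

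| r | Randomized | Power |
|---|---|---|
| 11.2% | 240 | 81.3% |
| 12.3% | 237 | 80.9% |
| 16.4% | 226 | 79.2% |
| 29.3% | 191 | 73.1% |

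This table tests a planning assumption; it is not part of the arithmetic error.

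**The case against.** The strongest reply is that little follows in practice. The shortfall at 220 is 0.6 to 1.7 power points. The operative target is 300 enrolled, which gives 79.8% by the formula and about 80.4% at 114 per arm with the Newcombe or Agresti-Caffo interval. The inputs are rounded planning values: a common rate near 27.5% would give 110 per arm, and uncertainty about the rate outweighs 4 to 6 subjects per arm. All of this stands as a limit on importance. It does not rescue the figure: the protocol states 30%, and its own reference value of 31.5% would need 119 per arm.

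A second reply is that the dropout margin exists when judged against the protocol's own 220: 229.5 − 220 = 9.5 subjects, about 4%. That is correct, but 220 does not give the 80% power that the margin is meant to protect.

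A third is that randomized dropouts counted as non-responders stay in the denominator. This also stands. The missing margin matters only for losses before randomization beyond the 15% and 10% already allowed for, and for randomized subjects who never enter mFAS.

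Finally, the Week 24 remission scenarios are a separate matter. The protocol lists all four rates and explains its choice of 15%, and two of the four give more than 80% power at 300. They show how sensitive the plan is, not that the arithmetic is wrong.

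**Conclusion.** The point holds and is minor. On the stated inputs, 110 per arm gives about 78 to 79% power. Reaching 80% takes 114 to 116 per arm by most methods, 116 by the unpooled formula, and 117 only with the n−1 variance. At 300 enrolled, power is about 80% with essentially no allowance for further loss. Type I error is not affected.

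This rests on the protocol's 30% rate in both arms, its 15% and 10% losses before randomization, and a two-arm calculation that ignores the country strata used in the primary analysis (SAP 6.1). No non-inferiority method tried on these inputs yields 110.

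**What to change.** Keep the target of 300 and restate Protocol 9.4.1 to say that:

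- 110 per arm gives about 78 to 79% power;
- 80% power needs about 114 to 116 per arm (116 per arm, 232 in total, by the unpooled formula), or about 299 to 304 enrolled before any dropout;
- 300 enrolled gives about 229 randomized and about 80% power, with essentially no dropout margin.

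Name the interval method behind whichever figure is kept. The cost is one or two sentences and a slightly less favourable power statement. No extra patients are needed, and the margin, endpoint and analysis do not change.

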#### 9.5 Study discontinuation criteria

The entire study will be discontinued if either of the below criteria is applicable. The Lead Principal Investigator shall notify the principal investigator of each study site promptly upon his/her decision to discontinue the study. Then, each principal investigator shall promptly notify his/her subjects, and provide appropriate medical intervention and take other necessary actions.

• The number of subjects enrolled is much below the target number or many subjects achieve SDAI remission at Week 24 so that only a small group of the subjects are assigned to ARM-2 or ARM-3; from either of which the Lead Principal Investigator or Study Biostatistician judges it difficult to achieve the goal even if the study continues.

#### 9.6 Handling of study data

Subjects with missing data at an assessment timepoint of SDAI remission, ACR20, ACR50, and ACR70 response, HAQ remission, and structural remission due to study discontinuation or other relevant reasons will be considered as a "non-responder" at the specific timepoint. Any missing data on SDAI, CDAI, DAS28-ESR, and DAS28-CRP will be considered as missing at the specific timepoint. A missing data on the assessment of SDAI, CDAI, DAS28-

ESR, DAS28-CRP, and mTSS will be complemented with the last observation carried forward (LOCF).

## 9.7 Data evaluation

Prior to the final analysis, the data obtained before randomization will be summarized in the course of the study for the purpose of presentations at academic conferences. The summary of the data are allowed to be presented at academic conferences after the completion of subject enrollment in principle. This study will not be biased as the data obtained before randomization are collected.

## 9.8 Deviation from statistical analysis plan

If there is a revision required in the statistical analysis plan after the start of this study, the Lead Principal Investigator shall determine the effect of such revision on this study, and how to apply such revision. The details of the revision shall be specified in the clinical study report of this study.

#### 10 Direct access to source data and document

Principal investigators and study sites must allow direct access to the study-related source data and documents during study monitoring, audit, Certified Review Board's/Ethical Review Board's review, and authorities' inspection.

## 11 Monitoring and audit

#### 11.1 Monitoring

Monitoring will be performed on this study to ensure the compliance with ICH-GCP, the Clinical Trials Act, study protocol, and all other applicable regulations and procedures, accurate data collection, appropriate informed consent process, and adequate safety assurance of subjects.

Monitoring will include central monitoring of EDC data and on-site monitoring, both of which will be conducted in accordance with the monitoring plan to be separately set out.

#### 11.2 Audit

To enhance the assurance activities of this intervention study, audit staff will examine this study to ensure its compliance to ICH-GCP, the Clinical Trials Act, the study protocol, and all other regulations and procedures.

## 12 Ethics

## 12.1 Benefits and disadvantages to subjects

It is unlikely that this study offers direct benefits to the subjects since the study treatment is a standard treatment within usual clinical practice. However, the results of the study to

establish the optimal usage of ADA and MTX is expected to eventually generate benefits for RA patients in the future.

Meanwhile, potential disadvantages associated with this study may be ADRs of MTX and ADA, as with other standard treatments. Also, investigational blood sampling may become a disadvantage. However, this is only additional collection of very small volume blood to routine blood collection in clinical practice; thus, the risk thereof will be negligible.

## 12.2 Informed consent

## 12.2.1 Inform patient

Before enrollment of each patient, the principal investigator/sub-investigator shall hand out to the patient the informed consent document approved by the Certified Review Board (Japan)/Ethical Review Board (South Korea and Taiwan), and orally describe in words easy to understand;

- 1) The study title, the research aspect of the study, and the fact that the study is approved by the head of the study site;
- 2) The name of the study site, and the name of the principal investigator;
- 3) Study objective and purpose:
- 4) Study methodology (including the treatment given in the study, the probability to be randomized to each group, study procedures including all invasive procedures, and the purpose for use of samples and information obtained from subjects), as well as the anticipated duration of subjects' enrollment in this study, and the number of subjects taking part in the study;
- 5) Reason for the patient to be selected as a study subject;
- 6) Subjects' responsibilities, the experimental aspect of this study, the burden on subjects, and anticipated risks and benefits;
- 7) Subjects' rights to withdraw their consent at any time even after having consented to start or continue the study;
- 8) Assurance that in no event will subjects or any other related-party be penalized in any way for not consenting to start or continue the study, or withdrawing their consent;
- 9) Method used to publicly release study-related information;
- 10) Subjects' rights to obtain or review the protocol and other materials on study procedures within the scope that would not interfere with the protection of other subjects' personal information or the originality of this study, and the method to obtain or review such materials;
- 11) Handling of personal information, etc. (Protection of confidential information that could track down subjects' identifies unless otherwise required by laws, and protection of subjects' identity even if the study results are publicly released);
- 12) Method for storage and disposal of samples and information;
- 13) Source of funding for the study, conflict of interest and individuals' profits concerning the study at the site, and conflict of interest among study staff;

- 14) Handling of consultation requested by subjects and other related personnel (liaison for subjects' further inquiry on information concerning this study and the subjects' rights thereto related, or subjects' reporting of health damage that occur in the study);
- 15) Economic burden or benefit for subjects, and the contents thereof;
- 16) Other therapeutic options if the study involves a medical intervention beyond the scope of ordinary clinical practice;
- 17) Medical intervention to be provided to subjects after the study if the study involves a medical intervention beyond the scope of ordinary clinical practice;
- 18) Handling of study results concerning individual subjects (including incidental findings) if there is a possibility to obtain important information concerning subjects' health, genetic characteristics transmitted to the descendants, or other finding pertinent to this study;
- 19) Health damage that could occur in the study and the presence/absence and contents of any compensation program if the study involves invasive procedures;
- 20) Possible uses of subjects samples and information for future researches that are not identified at the time of subjects' informed consent, possible transfer of subjects' samples and information to other research facilities, and the contents thereof anticipated at the time of informed consent;
- 21) Disclosure of subjects' samples and information to persons conducting monitoring/audit, Certified Review Board/Ethical Review Board, and regulatory agency to an extent necessary and under an assumption that subjects' confidentiality will be protected, if the study involves invasive procedures(except for minor invasive procedure), and that the signature on the consent form is construed as the subject's and his/her legally-acceptable representative's acceptance to allow for direct access to such source documents;
- 22) Procedures by which any information that could affect the subjects' willingness to continue taking part in the study will be communicated to subjects and their legally-acceptable representatives at an appropriate timing; and
- 23) Conditions by which subjects' withdrawal from the study can be anticipated, and the reason therefor.

## 12.2.2 Consent

Request the patient to take part in this study only after completing the patient briefing and confirming that the patient has fully understood the study contents.

Upon the subject's consent to take part in the study, the consent form approved by the Certified Review Board (Japan)/Ethical Review Board (South Korea and Taiwan) should be used to record the name of the briefing physician, the name of the consenting patient, the date of consent, and to have signature of the physician and patient. Three copies of the identical consent form should be in principle prepared; 1 copy should be handed to the patient, 1 should be retained by the principal investigator, and 1 should be submitted to the on-site study secretariat while the actual procedures should be in compliance with each site's operating procedures.

## 12.2.3 Representative

A legally-acceptable representative needs to be assigned and consent in writing on behalf of a subject aged <20 years in Japan and <19 years in South Korea at the time of informed consent.

Even if the consent is to be obtained from such a legally-acceptable representative, the patient should still be requested to take part in this study after completing the patient briefing and confirming that the patient has fully understood the study contents; in which case, a written consent should be separately obtained from the patient.

## 12.3 Protection of subjects' privacy and patient identification

The data concerning a subject enrolled in this study will be entered in EDC after anonymized and encoded to a subject ID issued at the registration; subject's name, address, telephone number, and other information that could directly identify an individual subject will not be recorded in the database.

Also, in no event shall any information concerning subjects' privacy be divulged to a third party by a study staff exposed to such information during this study.

## 12.4 Certified Review Board/Ethical Review Board

## 12.4.1 Approval

Before conducting this study, the Lead Principal Investigator shall submit the protocol, written information for patient, written informed consent form, and other necessary documents to the Certified Review Board and obtain its approval to conduct this study. Also in South Korea and Taiwan, the principal investigator shall submit the necessary documents to the Ethical Review Board, and obtain its approval to conduct this study. Upon obtaining approval of the site, the approval format shall be retained at the site, and its copy shall be sent to the study secretariat (Operation Center).

